4.3.3 Limitations of the study design

As above, it is possible recording of A&G and referral has improved over time.

As an observational study, there is the potential for unmeasured confounding factors to affect the findings. It will not be possible to conclude any causal relationship between variations in locality or socio-demographic characteristics for A&G versus usual referrals due to our study being both exploratory and descriptive. Misclassification of cases, exposures, and covariates is possible but expected to occur at random and so not introduce a significant degree of bias.

There may be other locality-dependent portals available for primary care clinicians to access specialist input without requiring a formal referral, such as teledermatology services and applications such as Consultant Connect, which facilitate telephone contact with the consultant/specialist and may not be coded by the GP. The consequence of this is that there may be missed episodes of A&G, but we believe this to be the minority of cases or at the more urgent end of the spectrum of clinical presentations rather than our focus on elective care.

5 WORK PACKAGE 2 a&b (QUANTITATIVE)

This section of the protocol relates to Work Package 2 a&b and will be designed iteratively as findings from WP 1b and our work with our PPIE and stakeholders emerge. Permissions will be sought from the RDG Secretariat via the electronic Research Application Portal.

Study Title: Determining outcomes of the use of Advice and Guidance: a cohort study

5.1 OBJECTIVES, SPECIFIC AIMS & RATIONALE

The aim of this sub-study is to determine outcomes of the use Advice and Guidance (A&G) in primary care. Specific objectives are to:

- 2a. Describe outcomes of tracer conditions following A&G compared to initial direct (non two-week wait)* referral pathways
- 2b. Describe healthcare utilisation and patient burden (for example, further consultations, referrals or prescribing in primary care, unplanned admissions, outpatient appointments) comparing A&G and direct referral pathways.

*non 2 week wait means referrals that are not on fast-track suspected cancer pathways that are used for patients with suspected cancer

5.2 STUDY DETAILS

5.2.1 Study type

Descriptive and exploratory / hypothesis generating

5.2.2 Study design

Retrospective cohort

5.2.3 Feasibility counts

NIHR 158681BADGER			
Protocol Version 2.0 18/06/2024	CPMS: 58336	IRAS No: 333799	CPRD ID: 24_004022

A feasibility count between 2015 and 2023 indicates approximately 1.7million A&G requests for 975,000 individuals.

5.2.4 Outcomes to be measured

For WP2a, the outcome for those with an A&G and/or direct referral recorded will be the time to diagnosis from the first recorded A&G or direct referral to index diagnosis date.

For WP2b, outcomes will be guided by our PPIE and Stakeholder groups as well as emerging results from interviews with PCC's. They are likely to include in the 12 months following referral:

- i. Number of consultations recorded in primary care;
- ii. Number of prescriptions recorded in primary care;
- iii. Number of referrals recorded in primary care;
- iv. AE attendance recorded in HES AE
- v. Number of additional outpatient appointment recorded in HES outpatients
- vi. Overnight unplanned hospital admission recorded in HES APC (admitted patient care);
- vii. Mortality recorded in ONS.

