5.2.7 Definition of the study population

All individuals in the CPRD Aurum database, regardless of age, with a first recorded index tracer condition between 01/01/2015 to 31/12/2022 and 24 months prior registration in CPRD Aurum. We will compare outcomes for patients with a recent history of A&G to those with direct referral, stratified by tracer condition. A&G and direct referrals will be obtained from primary care records in the 24 months prior to index (first diagnosis) date. Patients with both A&G and direct referral will be classified based on whichever happened first. We will include age at index date, gender, neighbourhood deprivation, geographical region, and ethnicity, as common covariates for all analyses as well as covariates (e.g. multiple long term conditions) specific to each tracer condition. There is no comparison or control group.

The tracer conditions will be informed from the work in WP1, including interviews with PCCs, and the experiences and advice of our PPIE and Stakeholder groups.

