5.3 DATA / STATISTICAL ANALYSIS

For WP2a, the outcome for those with an A&G and/or direct referral recorded will be the time to diagnosis from the first recorded A&G or direct referral to index diagnosis date. We will calculate median (interquartile range) days to diagnosis from first recorded A&G or direct referral code and incidence rates per 1,000 person years and present with 95% confidence intervals. We will use flexible parametric survival analysis to compare A&G and direct referral on time to diagnosis. Flexible parametric survival analyses are preferred to Cox proportional hazards regression as they allow easier modelling of time-dependent effects and the ability to determine absolute risks of outcome. Exposure' will be the initial method of referral (A&G, direct referral) prior to index date. Hazard ratios will be presented as unadjusted and adjusted for covariates with 95% confidence intervals (CI).

For WP 2b, individuals with each index condition will be categorised as i) A&G only, ii) direct referral only, iii) A&G and direct referral, iv) no recorded A&G or direct referral in the 24 months before diagnosis:

- negative binomial or zero-inflated negative binomial regression will be used to estimate incidence rate ratios for the number of consultations, referrals and prescriptions in primary care, and number of outpatient appointments,
- robust Poisson regression will be used to compare A&E and unplanned admission in secondary care;
- flexible parametric survival analysis will estimate hazard ratios for mortality.

Rates or ratios will be presented as unadjusted and adjusted for covariates with 95% CI.

As part of the Study Within A Project (SWAP) (see Section 8), the impact of multimorbidity and frailty on decision to use A&G and its outcomes will be considered by including multimorbidity and frailty (defined by Charlson comorbidity index/number of prescriptions and electronic frailty index) as predictors and moderators of A&G outcome in the models.

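### The WP2b referral count treats the A&G and direct-referral pathways unequally, and the four groups in 5.3 do not cure this

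*Protocol*

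**What the plan says.** Objective 2b in Protocol 5.1 concerns healthcare use and patient burden, "comparing A&G and direct referral pathways". Section 5.2.4 introduces the WP2b outcomes with "They are likely to include in the 12 months following referral"; the third item is "Number of referrals recorded in primary care". The fifth item, "Number of additional outpatient appointment recorded in HES outpatients", carries a qualifier that the referral item lacks.

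Section 5.3 commits to negative binomial or zero-inflated negative binomial regression to "estimate incidence rate ratios for the number of consultations, referrals and prescriptions in primary care". For WP2b it says that "individuals with each index condition will be categorised as i) A&G only, ii) direct referral only, iii) A&G and direct referral", with a last group "iv) no recorded A&G or direct referral in the 24 months before diagnosis". Below these are called *A&G only*, *direct only*, *both* and *neither*.

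Section 5.2.7, on the WP2 population, has a different rule: "Patients with both A&G and direct referral will be classified based on whichever happened first". Section 5.3 applies exposure by initial method to the WP2a survival analysis and does not carry it into WP2b.

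No section says whether the index direct referral is counted, or which event starts the window for a patient who has both.

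**The concern.** For this one outcome, the exposure event and the outcome event can be the same kind of event. A direct referral opens follow-up in one pathway and is an outcome in the other.

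The grouping adds a second problem. Membership of *A&G only* or *both* depends on whether a direct referral was recorded before diagnosis, and that referral may lie inside the year over which referrals are counted. The exposure is then partly defined by the outcome.

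The stake is a policy question. Section 1.1.2 presents A&G as a way to avoid unneeded outpatient activity and additions to waiting lists. A count that charges A&G for each conversion, but gives it no credit for a referral avoided, does not measure that.

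**Working it through.** **The plan's own figures.** The plan gives no figure for the referral count. The only WP2 calculation (5.2.5: about 11,000 diagnoses, 5% with A&G, hazard ratio 1.15, 90% power) concerns time to diagnosis. By Schoenfeld's formula, two-sided 5%, it gives 0.892, which agrees with the stated 90%. This point does not affect it.

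**Step 1: three patients, counting strictly after the first event.**

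| Patient | Direct referrals used | Score |
|---|---|---|
| Direct referral on day 0, nothing further | 1 | 0 |
| A&G on day 0, direct referral on day 30 | 1 | 1 |
| A&G on day 0, settled by advice | 0 | 0 |

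Patients with equal use score differently, and patients with different use score the same.

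**Step 2: first-event comparison (5.2.7).** Inputs:
- c, the share of A&G patients converted to direct referral. Section 4.2.5 uses 50% to size WP1a confidence limits, and the surgical audit in 1.1.2 reports 61% deferred to outpatient clinic. Neither is a WP2 estimate.
- b, other direct referrals per patient in the year, taken as equal in both arms. The documents give no value, so a range of 0.2 to 2 is shown.

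Counting after the index event: IRR = (b + c)/b. Counting the index direct referral: IRR = (b + c)/(b + 1). At b = c = 0.5 these are 1.0/0.5 = 2.00 and 1.0/1.5 = 0.67.

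| b | c = 0.50: after index | c = 0.50: including index | c = 0.61: after index | c = 0.61: including index |
|---|---|---|---|---|
| 0.2 | 3.50 | 0.58 | 4.05 | 0.675 |
| 0.5 | 2.00 | 0.67 | 2.22 | 0.74 |
| 1 | 1.50 | 0.75 | 1.61 | 0.805 |
| 2 | 1.25 | 0.83 | 1.305 | 0.87 |

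With equal b and 0 < c < 1, the first ratio is always above 1 and the second always below 1.

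**Step 3: the four groups of 5.3.** The groups were simulated under these assumptions: exponential time from first event to diagnosis (median 180 days, truncated at 24 months), conversion spread evenly over 122 days (the window in 4.2.8), and Poisson background referrals at rate b in both arms. Referrals were counted for 365 days after the first event. *Both* here means A&G first. Patients whose direct referral came first and who later had A&G were not modelled.

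| c | b | *A&G only* v *direct only* | *Both* v *direct only* |
|---|---|---|---|
| 0.30 | 0.2 | 1.02 | 5.78 |
| 0.30 | 0.5 | 0.81 | 2.78 |
| 0.30 | 1 | 0.78 | 1.80 |
| 0.30 | 2 | 0.82 | 1.34 |
| 0.50 | 0.2 | 1.56 | 5.91 |
| 0.50 | 0.5 | 1.06 | 2.89 |
| 0.50 | 1 | 0.93 | 1.89 |
| 0.50 | 2 | 0.92 | 1.40 |
| 0.61 | 0.2 | 1.98 | 5.95 |
| 0.61 | 0.5 | 1.25 | 2.94 |
| 0.61 | 1 | 1.05 | 1.93 |
| 0.61 | 2 | 0.99 | 1.43 |

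At b = c = 0.5, *A&G only* v *direct only* moves from 1.06 to 1.49 if the median time to diagnosis is 60 days, and to 0.86 if it is 365 days. *Both* stays near 3 (3.01 and 2.85).

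*Both* is raised because a direct referral is a condition of entry. *A&G only* is pulled down because it can have no direct referral between A&G and diagnosis, and pushed up by conversions recorded after diagnosis. Which effect prevails depends on how quickly the condition is diagnosed, so the ratio need not be comparable across tracer conditions.

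**Step 4: the *neither* group.** These patients have no referral of either kind, so a window that starts at referral has no start date for them.

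**The case against.** The strongest objection is that 5.3 does not set a single A&G arm against a direct arm. An A&G converted before diagnosis goes into *both*, so *A&G only* is not bound to equal or exceed *direct only*. This stands, and it removes any fixed direction for that contrast. It does not restore equal counting: Step 3 shows a different distortion in its place.

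Second, the text does not say that the index referral is excluded, and for patients with both events the window might start at the direct referral. Section 1.3 also treats A&G as a type of referral. On that view each arm leaves out its own index event, and a conversion is a real second referral. The rule is indeed unclear. But 4.2.8 defines A&G requests and direct referrals as separate coded events, 5.2.8 adopts those definitions, and the window is worded as following referral. Even on the broader view the outcome measures further referrals only, not the referrals that each pathway used.

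Third, the outcome list is provisional, WP2 is to be designed iteratively, and counting rules often sit in an analysis plan. That lowers the urgency. However, the protocol itself sets the window, the groups and the rate ratio, and the problem comes from combining them.

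Fourth, with equal b the inclusive count gives a ratio below 1 for every c below 1. This is true. The inclusive ratio shows how many direct referrals A&G avoided, not whether avoiding them was good for patients. Downstream workload is also a legitimate question, which is why the further-referrals count should be kept as a secondary measure.

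**Conclusion.** The point holds as a defect of definition and grouping. On the plain reading the WP2b referral count leaves out the direct-referral patient's own referral and includes the A&G patient's conversion. The 5.3 groups then sort patients by referrals that can lie inside the outcome window. Under the assumptions shown, *both* v *direct only* is biased upward (1.34 to 5.95), and *A&G only* v *direct only* can fall on either side of 1 (0.78 to 1.98).

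A reader might infer that A&G is bound to appear to increase referrals, or that the direct-referral patient's referral is never counted. The documents support neither. The first follows only from the first-event comparison of 5.2.7 with similar background rates in the two arms. The second is an inference from wording that is silent on the index referral.

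The sizes are illustrative: b is assumed throughout, and c is borrowed from outside WP2, whose cohort contains only people later diagnosed with a tracer condition. The reversal at 2.00 v 0.67 needs equal b but no particular value of it. One of seven provisional outcomes is affected, but it bears directly on what A&G is meant to achieve.

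**What to change.** For the referral outcome in 5.2.4 (iii):

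1. Reconcile 5.2.7 with 5.3 by classifying exposure by the first event, A&G or direct referral, and use that event as the single time zero. Leave *neither* out of this contrast.
2. Count direct referrals over 12 months from and including time zero, so that the index direct referral scores one and an A&G request scores zero.
3. Replace the zero-inflated option with a count model suited to a minimum of one in the direct-referral arm. Robust Poisson regression, already planned for other WP2b outcomes, is one candidate.
4. Report referrals after the first direct referral, in both arms, as a secondary measure of further referrals.

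Steps 1 and 2 belong together: changing the count alone leaves the four-group contrast distorted.

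The cost is revised wording in 5.2.4, 5.2.7 and 5.3 and slightly more analysis work. No new data are needed, and section 5 says that permissions for WP2 are still to be sought.

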5.2.5 Sample size considerations

Taking multiple sclerosis as the example condition, we expect around 11,000 people to have a new diagnosis between 2015 and 2022 in CPRD (based on reported national incidence of 7,000 per year,²⁴ CPRD covering 20% of UK population and study period of 8 years). Based on the feasibility study in SLE, if 5% received A&G then we could detect a hazard ratio of 1.15 or more with 90% power at a 5% significance level. We expect other conditions to be more prevalent.

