Additional considerations that have been raised by our PPIE groups included: whether A&G can be used in the mental health sector and whether mental health conditions and learning disabilities can and should be considered during the use of A&G. PPIE members voiced concern about the process of A&G, questioning if it was worked into clinician's job plans or completed on an unfunded ad hoc basis and furthermore, how an increase in requests at scale might impact on capacity and other clinical activities and responsibilities. Members enquired if safeguards were in place to ensure queries were answered in secondary care and picked back up by clinicians in primary care. This will be considered in our qualitative and stakeholder work. In addition to SLE and MND, further potential targets for tracer conditions were suggested, including women's health conditions (endometriosis) that would network well with charities working to raise awareness.

NIHR 158681BADGER			
Protocol Version 2.0 18/06/2024	CPMS: 58336	IRAS No: 333799	CPRD ID: 24_004022

Recommendations for patient facing outputs were also suggested including materials for Patient Participation Groups newsletters, waiting room slide shows, text message templates with links to further information / videos. It was highlighted that all materials should be culturally appropriate and easily accessible.

We have had two further meetings with the BADGER group to support development of the patient-participant study information sheet, postcard, and topic guide. Incorporated changes included colour scheme, language used and imagery in the information guide.

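### The 90% power for a hazard ratio of 1.15 in section 5.2.5 is computed on all expected MS diagnoses, not on the WP2a analysis set, and has no reserve

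*Protocol*

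**What the plan says.** Section 5.2.5 (Sample size considerations) uses MS as its example: "we expect around 11,000 people to have a new diagnosis between 2015 and 2022 in CPRD". The count rests on 7,000 UK diagnoses a year and "CPRD covering 20% of UK population and study period of 8 years". The exposure share is borrowed from a feasibility study in another condition, SLE. From these inputs the section concludes that "if 5% received A&G then we could detect a hazard ratio of 1.15 or more with 90% power at a 5% significance level". It closes by expecting other conditions to be commoner, without giving a count for any.

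The WP2a analysis set is defined elsewhere:

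- Section 5.2.4 limits the outcome to patients with a relevant record: "For WP2a, the outcome for those with an A&G and/or direct referral recorded will be the time to diagnosis".
- Section 5.2.7 requires 24 months of registration before diagnosis, looks for A&G and referrals in those same 24 months, and stratifies by tracer condition.
- Section 5.2.7 also fixes the exposure of patients with both records: "Patients with both A&G and direct referral will be classified based on whichever happened first".
- Section 5.3 lists, for WP2b, a category with neither record. The protocol therefore expects some diagnosed patients to fall outside the WP2a comparison.

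**The concern.** The calculation treats every expected MS diagnosis as an analysed event and every A&G recipient as exposed. The WP2a rules can only reduce those numbers. The registration rule removes patients from both groups. The need for a coded request or referral removes those with neither. The first-event rule moves anyone referred before their A&G request into the comparator. Section 5.2.5 allows for none of these.

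The third rule is a live possibility on the protocol's own account. Section 4.2.8 plans to measure how often A&G follows a referral, and section 1.1.2 reports that some providers convert referrals into A&G.

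WP2a compares time to diagnosis between the two pathways, and section 10.1.2 sends the results to policy makers and commissioners. If the stated sensitivity is better than the real one, readers have the wrong yardstick for an inconclusive hazard ratio.

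**Working it through.** **Inputs.** Section 5.2.5 gives 7,000 diagnoses a year, 20% coverage, 8 years, 5% A&G, hazard ratio 1.15, 90% power and a 5% level. Sidedness is not stated; two-sided reproduces the figure, while one-sided gives 93.9%. Every analysed patient has the diagnosis, so events equal patients analysed.

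**Formulas (Schoenfeld).** With D events and exposed share p:

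- power = Φ(ln HR × √(D·p·(1−p)) − 1.960)
- detectable HR at 90% power = exp((1.960 + 1.2816) / √(D·p·(1−p)))
- events needed = (1.960 + 1.2816)² / (p·(1−p)·(ln HR)²)

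**The plan's own figure.** 7,000 × 0.20 × 8 = 11,200, which the protocol gives as about 11,000. With D = 11,000 and p = 0.05 (550 exposed):

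- √(11,000 × 0.0475) = 22.86
- 0.1398 × 22.86 − 1.960 = 1.235
- power 89.2%, detectable HR 1.152

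With D = 11,200, power is 89.7% and the detectable HR is 1.151. Exactly 90% needs about 11,325 events. The claim reproduces, with nothing in reserve.

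**Applying the WP2a rules one at a time.** The protocol gives no loss shares, so those below are assumed.

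| Rule and assumption | Analysed | Exposed | Power for HR 1.15 | Detectable HR, 90% power |
|---|---|---|---|---|
| Neither record dropped, 550 stay exposed: 80% analysed | 8,800 | 550 | 88.8% | 1.15 |
| Same, 60% analysed | 6,600 | 550 | 88.1% | 1.16 |
| Both groups lose 10% (e.g. registration) | 9,900 | 495 | 85.8% | 1.16 |
| Both groups lose 20% | 8,800 | 440 | 81.5% | 1.17 |
| Both groups lose 30% | 7,700 | 385 | 76.2% | 1.18 |
| 25% of A&G users had the referral first | 11,000 | 412.5 | 79.5% | 1.18 |
| 50% of A&G users had the referral first | 11,000 | 275 | 62.9% | 1.22 |

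As one combined example, suppose 20% fail registration, 70% of the rest have a record, and 25% of A&G users are reclassified. Then 11,000 × 0.8 × 0.7 = 6,160 are analysed and 550 × 0.8 × 0.75 = 330 are exposed. Power is 69.5% and the detectable HR is 1.20.

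**What the 5% is a share of.** The first two rows assume 5% of all cases. If it is instead 5% of patients with a coded record, and 60% of cases have one, the exposed group is 0.05 × 6,600 = 330, power is 69.7% and the detectable HR is 1.20. The same loss costs about 1 point under one reading and about 20 under the other.

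**Needed per tracer.** For HR 1.15 at 90% power, the events formula gives about 11,325 analysed cases if 5% are A&G-first, about 14,900 if 3.75% are, and about 22,100 if 2.5% are. If 20% of diagnoses fail registration, the first figure becomes 11,325 / 0.8 ≈ 14,160 new diagnoses.

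**The case against.** The strongest reply is that nothing has been miscalculated. The figure follows from its stated inputs, is worded conditionally, and illustrates one example condition. WP2 is described as exploratory and hypothesis generating (5.2.1). Its design is iterative, with data permissions still to be sought (section 5). Results will be hazard ratios with confidence intervals, and no decision rule hangs on a null result. All of this stands, and it makes the point a restatement rather than a flaw in the design.

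The comparator group is also so large that shrinking it hardly matters. A reader might infer that the power holds only if all 11,000 cases are analysed. That is too strong: if 550 remain exposed, power stays within about two points of 90% even with 60% analysed.

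A reader might also infer that the rules exclude or reclassify a large number of patients, or that 1.15 should give way to one new figure. The documents support neither. They give no size for any excluded or reclassified group and no denominator for the 5%. The SLE feasibility study is not shown, and its 5% might already refer to referred patients or to A&G-first patients.

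Finally, section 9.1 says "In addition to SLE and MND, further potential targets for tracer conditions were suggested", and a reader might conclude that these conditions are too rare for WP2a. The protocol gives no incidence for them and has not chosen its tracers, so that cannot be shown from the documents.

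The reply does not remove the mismatch. The section states a power for a population other than the one WP2a will compare, and leaves no margin for the difference.

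**Conclusion.** The power statement is arithmetically correct (89% to 90%) but describes all expected MS diagnoses rather than the WP2a analysis set. Because exactly 90% already needs slightly more events than the plan expects, any loss of exposed patients takes power for HR 1.15 further below the claim.

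The A&G-first count drives the size of the shortfall. Across the single-rule losses tabulated, power runs from about 88% down to about 63%, and the detectable hazard ratio from about 1.15 to 1.22. That spread reflects assumed loss shares and is not an estimate for MS.

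The closing remark that other conditions should be commoner does not fill the gap. The calculation runs on new diagnoses, not prevalence. WP2a is stratified by tracer, so each condition needs an adequate count of its own, and none is given.

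**What to change.** In section 5.2.5:

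1. Restate the power or detectable hazard ratio from the number expected to meet the registration and coded-record rules and the number expected to be A&G-first. Show it as a range over stated assumptions.
2. Say what the 5% is a share of (all diagnoses, those with a coded A&G or referral, or those with A&G first), and that the test is two-sided.
3. Replace the closing remark about other conditions with the number of new diagnoses each tracer needs for the stated hazard ratio.

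The cost is a rewritten paragraph and a somewhat less favourable stated figure. No extra patients are needed. Because WP2 permissions are still to be sought, the change can be made before that application.
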